During the placebo-controlled phase, treatment-emergent adverse events (TEAEs) were balanced across treatment groups while the percentages of patients with TEAE leading to treatment discontinuation were reported with a slightly higher incidence in the teriflunomide groups. The most frequently reported TEAEs with an increased incidence with teriflunomide as compared to placebo were: alopecia, nausea, diarrhea, and alanine aminotransferase (ALT) increased. Most cases of alopecia were reported as hair thinning, decreased hair density, hair loss, associated or not with hair texture change with a dose-effect. There was no complete hair loss reported in the entire clinical program. Most cases were mild to moderate, reported during the first 6 months, lasting for about 4 months, and resolving without corrective therapy, while the patients continued the study treatment.

Events of nausea and diarrhea were reported with a higher frequency in both teriflunomide groups than in the placebo with a dose effect. They appeared early after initiation of treatment. They were rarely considered as serious and led to treatment discontinuation in only a few patients.

There was no signal for hepatic toxicity in pre-clinical studies. Mild increases in transaminases, ALT below or equal to 3 x upper limit of normal (ULN), were more frequently seen in teriflunomide-treated groups as compared to placebo. The frequency of elevations above 3 x ULN and higher was balanced across treatment groups.

Overall, the clinical trial data does not provide evidence for an increased risk of clinically relevant drug induced liver injury with teriflunomide.

Pancreatic disorders were reported with low incidences, were balanced across treatment groups and led to treatment discontinuation in few patients.

A mean decrease in white blood cell (WBC) counts was observed (mainly neutrophil and lymphocyte count decrease) with a small dose response. The mean decrease occurred during the first 6 weeks, followed by stabilization over time on-treatment, with a magnitude not exceeding 15%. The mean decrease was less pronounced in hemoglobin ( $\leq 3\%$ ) and platelets ( $< 10\%$ ) as compared to baseline.

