2.1.4.1 Adverse events variables

Adverse event observation period

- Treatment-emergent adverse events are adverse events that developed or worsened or became serious during the treatment-emergent adverse event period in the open-label period of the study.
- Posttreatment adverse events are adverse events that developed or worsened or became serious during the posttreatment period in the open-label period of the study.

All adverse events, including serious adverse events (SAEs) and adverse events of special interest (AESI) will be coded to a lower-level term (LLT), preferred term (PT), high-level term (HLT), high-level group term (HLGT), and associated primary system organ class (SOC) using the version of Medical Dictionary for Regulatory Activities (MedDRA) currently in effect at Sanofi at the time of database lock.

Record the occurrence of adverse events (including serious adverse events and AESI) from the time of signed informed consent until the end of the study.

AESIs include the following terms:

- Gastrointestinal disorders (Nausea and diarrhea)
- Hepatic disorders
- Pancreatic disorders
- Bone marrow disorders
- Infections and Infestations
 - A specific analysis of Covid-19 related adverse events will be performed, using the search terms described in Appendix D
- Hypersensitivity
- Severe skin reaction
- Malignancy
- Hypertension
- Cardiac Arrhythmias
- Pulmonary disorders (ILD)
- Embolic and Thrombotic
- Hemorrhage
- Peripheral neuropathy
- Convulsions
- Alopecia
- Psychiatric disorders

Additional AESIs may be identified through the ongoing studies. The complete list of AESIs and details of the grouping algorithm will be finalized prior to the Database Lock (DBL).

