- By-patient listing of TEAEs leading to treatment discontinuation showing treatment group, patient identified, age, gender, race, primary SOC decode, PT decode, verbatim (diagnosis), onset date and study day, date of death (if relevant), recovery date/time, event duration, outcome, intensity/grade, relationship to study treatment, action taken with study treatment and corrective treatment/therapy, AE serious criteria, flag for AE status, flag for seriousness, and Covid-19 related flag.

AESIs summaries

- All treatment emergent adverse events of special interest, by primary SOC, HLGT, HLT, and PT, showing number (%) of patients with at least one TEAE sorted by SOC internationally agreed order. The other level (HLGT, HLT, PT) will be presented in an alphabetic order.

In addition, the following exposure adjusted analyses will be performed for treatment emergent adverse events with pre-specified monitoring adverse events.

The frequency of TEAEs across pre-defined time intervals will be provided for the treatment emergent AESIs, where the time intervals will be defined as: $>0 \leq 1$ week, $>1 \leq 4$ week, $>4 \leq 12$ weeks, $>12 \leq 24$ weeks, $>24 \leq 36$ weeks, $>36 \leq 48$ weeks, $>48 \leq 60$ weeks, $>60 \leq 72$ weeks, $>72 \leq 84$ weeks, $>84 \leq 96$ weeks, $>96 \leq 108$ weeks, $>108 \leq 120$ weeks, $>120 \leq 132$ weeks, $>132 \leq 144$ weeks, $>144 \leq 156$ weeks, $>156 \leq 168$ weeks, $>168 \leq 180$ weeks, $>180 \leq 192$ weeks and >192 weeks for open-label period. In each time interval, the denominator for calculation of percentage will be the number of patients exposed at the beginning of the time interval who did not report the given TEAE in the preceding intervals and the numerator will be the number of patients with at least one TEAE occurring in this time interval. Only the first event will be counted and all recurrent events will not be included.

Analysis of posttreatment adverse events

- All posttreatment adverse events by primary SOC and PT, showing the number (%) of patients with at least 1 posttreatment adverse event, sorted by the internationally agreed SOC order and decreasing incidence of PTs within each SOC.
- All posttreatment serious adverse events by primary SOC and PT, showing the number (%) of patients with at least 1 posttreatment serious adverse event, sorted by the internationally agreed SOC order and decreasing incidence of PTs within each SOC.

Long-term Safety Analysis

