Long-term safety of teriflunomide exposure will also be analyzed by including all teriflunomide exposure, ie, from randomization in the double-blind period in the teriflunomide group and from start in the open-label period in the placebo group, for the complete study population analyzed in one overall group. Key safety analyses on TEAEs, SAEs, TEAEs leading to treatment discontinuation and AESIs.

Safety Subgroup Analysis

Safety subgroup analyses will be performed for key tables of TEAEs/SAEs/AESIs and TEAEs leading to treatment discontinuation during the treatment-emergent adverse event period in the open-label period by:

- Intrinsic factors
 - Age group at study consent of the double-blind period (<13, ≥13 years)
 - Gender
 - Race
 - Pubertal status (at study consent, and at disease onset)
 - Baseline weight group in the double-blind period (≤40, >40 kgs)
 - MS subtypes (relapsing-remitting MS, other forms)
 - High disease activity at baseline (defined as 2 or more relapses in the past year of screening, and 1 or more Gadolinium enhancing lesions on baseline MRI of the double-blind period) (Yes, No)
- Extrinsic factors
 - Region (as defined in [Section 2.5.5](#)).

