Time to onset of the initial ALT and AST elevation (>3 x upper limit of normal range [ULN]) and total bilirubin elevation (>2 x ULN) (time to first observation of ALT >3 x ULN or total bilirubin >2 x ULN, whichever comes first) will be analyzed using Kaplan-Meier estimates, presented by treatment group. Consideration should be given to the impact of the spacing of scheduled tests. A graph of distribution of peak values of ALT versus peak values of total bilirubin will also be

presented. Note that the ALT and total bilirubin values are presented on a logarithmic scale. The graph will be divided into 4 quadrants with a vertical line corresponding to 3 x ULN for ALT and a horizontal line corresponding to 2 x ULN for total bilirubin.

Listing of possible Hy's law cases identified by treatment group (eg, patients with any elevated ALT > 3 x ULN, and associated with an increase in bilirubin \geq 2 x ULN), presented with ALT, AST, alkaline phosphatase, total bilirubin, and the following complementary parameters: conjugated bilirubin and prothrombin time/international normalized ratio, creatine phosphokinase and serum creatinine.

Summarize the normalization by parameter (to \leq 1 x ULN or return to baseline) of elevated liver function tests by categories of elevation (3 x, 5 x, 10 x, 20 x ULN for ALT and AST, 1.5 x ULN for alkaline phosphatase, and 1.5 x and 2 x ULN for total bilirubin), with the following categories of normalization: never normalized, normalized despite treatment continuation of IMP, or normalized after IMP discontinuation. Note that a patient will be counted only under the maximum elevation category.

Proportion of patients with ALT > 1 x ULN and ALT > 2 x ULN at post-baseline visits will be presented by treatment group.

Summarize the incidence of liver-related adverse events by treatment group. The selection of preferred terms will be based on the hepatic disorder SMQ.

TSH

TSH will also be summarized for each study assessment by treatment group.

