2.5.3 Windows for time points

Time window for MRI measurements and SDMT will be used to capture data collected between visits. It is defined in [Table 4](#) and [Table 5](#). Baseline values will be the baseline defined in the double-blind period of the study. All days in the visit window tables for double-blind period ([Table 4](#) and [Table 6](#)) and the open-label period ([Table 5](#) and [Table 7](#)) are relative to the first dose date in each period respectively.

Table 4 - Visit window for MRI variables and SDMT in the double-blind period

Week	Visit	Target day	Schedule A^a	Schedule B^b
0	Baseline	1	Up to 1st dose date	Up to 1st dose date
24	Visit 8	169	after 1 st dose date - 252	after 1 st dose date -210
36	Visit 10	253	Not applicable	211 - 294
48	Visit 12	337	253 - 420	295 - 420
72	Visit 16	505	421 - 588	421 - 588
96	Visit 20	673	589 - Last double-blind dose date + 60 days and before 1st open label dose	589 - Last double-blind dose date + 60 days and before 1st open label dose

^a SDMT and MRI variables for patients without MRI assessment for Week 36

^b MRI variables for patients with MRI assessment for Week 36

Table 5 - Visit window for MRI variables and SDMT in the open-label period

Week	Visit	Target day	SDMT	MRI variables
0	OL transition visit	1	Up to the first dose in OL period	Up to the first dose in OL period
24	OL Visit 7	169	after 1st open-label dose date - 252	Not applicable
48	OL Visit 11	337	252 - 420	after 1st open-label dose date – 504
72	OL Visit 15	505	421 – 588	Not applicable
96	OL Visit 19	673	589 – 756	505 – 840
120	OL Visit 23	841	757 – 924	Not applicable
144	OL Visit 27	1009	925 – 1092	841 – 1176
168	OL Visit 31	1177	1093 – 1260	Not applicable
192	OL Visit 35	1345	1261 - Later of the Last open-label visit date or the 1st dose date in optional additional extension period	1177 - Later of the Last open-label visit date or before 1st dose date in optional additional extension period

For multiple records within a visit window, the one closest to the targeted visit date will be used.

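### The AESI-by-interval table is clocked from open-label entry, so for teriflunomide/teriflunomide patients the early bins are not drug start and repeats of double-blind events count as first events

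*SAP*

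**What the plan says.** - **Clock.** The AESIs summaries in SAP 2.4.5.1 set bins from the first week up to "weeks and >192 weeks for open-label period". SAP 2.1.4.1 restricts TEAEs to events that "developed or worsened or became serious during the treatment-emergent adverse event period in the open-label period of the study", and SAP 2.1.4 starts the treatment epoch at the first open-label dose.
- **Who is at risk, and what counts.** The denominator of each bin is the exposed patients "who did not report the given TEAE in the preceding intervals". For the numerator, "Only the first event will be counted and all recurrent events will not be included".
- **Columns.** SAP 2.3.3 and 2.4.5 present safety by sequence (placebo/teriflunomide and teriflunomide/teriflunomide) and for both sequences together.
- **Routes into open label.** Protocol 5.1 and 8.1 allow entry after a confirmed relapse beyond the 8-week PK run-in, after high MRI activity (Week 36 at the earliest), or on completing 96 weeks.
- **Long-term analysis.** SAP 2.4.5.1 adds: "Long-term safety of teriflunomide exposure will also be analyzed by including all teriflunomide exposure". Exposure runs from randomization in the teriflunomide arm and from open-label start in the placebo arm, as one group. The content is given only as key analyses of TEAEs, SAEs, discontinuations and AESIs.
- **Liver curves.** SAP 2.4.5.3 plans Kaplan-Meier estimates of "Time to onset of the initial ALT and AST elevation" and of bilirubin elevation, by treatment group. It gives no time origin.

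**The concern.** A table of first events by time since start is normally read as an onset profile on drug. Here the same bin label means different things in the two sequences. For a former placebo patient the first-week bin is the first week on teriflunomide. For a former teriflunomide patient it is some point between about Week 8 and Week 96 of treatment, in someone who stayed on study long enough to reach open label.

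The look-back has the same limit. A patient who had the event on double-blind teriflunomide counts as event-free at open-label entry, and a second episode enters the table as a first one.

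This matters because the protocol describes several listed AESIs as early in adults. Section 3.1.2.2 says of alopecia: "Most cases were mild to moderate, reported during the first 6 months, lasting for about 4 months". It places nausea and diarrhea soon after treatment starts. Both groups of events are on the AESI list in SAP 2.1.4.1. A reader of the overall column could take their early risk on teriflunomide to be lower than it is in patients starting the drug.

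**Working it through.** **1. Minimum prior drug.** Total treatment from randomization is 192 weeks (Protocol 5.1.1). The run-in that must pass before a relapse switch is 8 weeks (Protocol 5.1).

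192 − 8 = 184 weeks

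This reproduces the maximum open-label duration stated in SAP Appendix C and in the notes to the Protocol 1.4 flow chart. Planned prior teriflunomide in the teriflunomide/teriflunomide sequence therefore runs from about 8 weeks (earliest relapse switch) to 96 weeks (completers).

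**2. A check on the bins.** Adding the 4-week elimination epoch (SAP 2.1.4), 184 + 4 = 188 weeks. On an open-label clock the bin beyond 192 weeks should be empty, barring delays. This does not alter the reading of the clock, but it is a further reason to state it.

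**3. Share of new starters in the overall column.** Planned numbers are 55 placebo and 110 teriflunomide (Protocol 5.1). With open-label entry rates a (placebo) and b (teriflunomide), s = 55a / (55a + 110b). The entry rates are assumptions.

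| a | b | s |
|---|---|---|
| 100% | 100% | 55/165 = 33.3% |
| 100% | 80% | 55/143 = 38.5% |
| 80% | 100% | 44/154 = 28.6% |
| 95% | 75% | 52.25/134.75 = 38.8% |

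**4. Early-bin rate in the overall column.** Let p be the risk in new starters and q the risk in already-exposed patients, both assumed. The overall rate is s·p + (1 − s)·q. With s = 1/3 this is (p + 2q)/3.

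| p | q = 0 | q = 1% | q = 2% |
|---|---|---|---|
| 5% | 1.7% | 2.3% | 3.0% |
| 10% | 3.3% | 4.0% | 4.7% |
| 20% | 6.7% | 7.3% | 8.0% |

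Letting entry vary as in step 3, p = 10% gives from 0.286 × 10% = 2.9% (q = 0) to 0.388 × 10% + 0.612 × 2% = 5.1% (q = 2%). With the clock at the first teriflunomide dose, both arms enter the first bin as new starters and the pooled rate is p.

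**5. Recurrences tabulated as first events.** As an illustration, suppose 10% to 20% of the 110 teriflunomide patients had a given AESI in the double-blind period, all entered open label, and 20% to 50% of them had it again. The count runs from 110 × 0.10 × 0.20 = 2.2 to 110 × 0.20 × 0.50 = 11, so about 2 to 11 patients. None of these rates is in the documents.

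**The case against.** The strongest reply is about scope. This SAP serves the open-label report. SAP 2 says the double-blind data were handled in a separate SAP, and counting the first event within the open-label period follows the SAP's own TEAE definition. The safety analysis is descriptive. Results are shown by sequence, so the placebo/teriflunomide column gives early onset on a correct clock. The Long-term Safety Analysis already covers exposure from first drug and names AESIs. It lists no individual tables, so silence about the interval table does not show that it is excluded.

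Most of this stands, and it rules out several stronger readings that a reader might infer:

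- **That every column dilutes early harm.** Only the overall column mixes the groups. The teriflunomide/teriflunomide column is wrongly clocked as an onset profile, and the placebo/teriflunomide column is sound.
- **That the liver curves start at open-label entry.** SAP 2.4.5.3 states no origin. The sentence in SAP 2.5.3 that days "are relative to the first dose date in each period respectively" governs the visit-window tables and does not set the origin of a time-to-event curve. SAP 2.4.5.3 also plans liver abnormalities by duration of exposure.
- **That early exposure in the teriflunomide arm goes untabulated.** The double-blind SAP is not among the documents, so this cannot be said.
- **That the overall rate falls to one third.** That is the limiting case, with no risk after early exposure and equal entry.
- **That the overall column should be dropped.** That is a presentation preference, and it is unnecessary when both sequences are shown.

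The reply does not remove the gap. Placebo/teriflunomide holds only 55 of the 165 planned starts on teriflunomide. A separate double-blind report cannot give one onset profile across both periods. As written, the long-term analysis commits to neither an interval table nor a first-event rule over all time on drug.

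**Conclusion.** The point holds for the AESI interval table. Its clock and look-back are confined to the open-label period, so teriflunomide/teriflunomide patients enter the first bin after about 8 to 96 weeks of planned drug and their recurrences can be counted as first events. Both follow from the SAP's wording and the protocol's entry rules.

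The size depends on assumptions. New starters make up about one third of the overall column at 2:1 with equal entry, and 29% to 39% over the entry rates tried. An assumed 10% early risk in new starters would appear there as 3.3% to 4.7% for an already-exposed risk of 0 to 2%. The 2 to 11 recurrences are illustrative only.

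For the liver curves the finding is an unstated origin and no more. Efficacy conclusions are not affected. The change is worth making because the alternative rule is clearer and uses data already collected.

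**What to change.** In the Long-term Safety Analysis of SAP 2.4.5.1, add the AESI-by-interval table with these rules:

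1. Time zero is the first teriflunomide dose: the first double-blind dose in the teriflunomide arm and the first open-label dose in the placebo arm.
2. The at-risk condition ("who did not report the given TEAE in the preceding intervals") and the first-event rule apply over all time on teriflunomide, across both periods.

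The open-label-clock table may stay as planned, with a note that it is to be read by sequence and that time zero is drug start only for placebo/teriflunomide.

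In SAP 2.4.5.3, state the time origin of the liver time-to-onset curves, and use the first-teriflunomide origin for the version in the long-term set.

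The cost is SAP wording plus one more programmed table and curve. No new data are needed.

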2.4.5.2 Deaths

The following summaries of deaths will be generated for the safety population.

- Number (%) of patients who died by study period (on-study, on-treatment, poststudy).
- Treatment-emergent adverse events leading to death (death as an outcome on the adverse event case report form page as reported by the Investigator) by primary SOC, HLGT, HLT, and PT showing number (%) of patients sorted by internationally agreed SOC order, with HLGT, HLT, and PT presented in alphabetical order within each SOC.

- By-patient listing of deaths showing treatment group, patient identified, age, gender, race, duration of exposure, date of death, primary reason of death.

2.4.5.3 Analyses of laboratory variables

The summary statistics (including number, mean, median, Q1, Q3, standard deviation, minimum and maximum) of all laboratory variables (central laboratory values and changes from baseline) will be calculated for each visit or study assessment (baseline, each postbaseline time point, last on-treatment and/or minimum and maximum value during the treatment-emergent adverse event period) by treatment group. Mean changes from baseline with the corresponding standard error will be plotted over time (at same time points) in each treatment group for laboratory parameters of primary interest. This section will be organized by biological function.

PCSA will be assessed based on age group at each visit. After subjects turn to be adult, the adult criteria will be applied. The incidence of PCSAs (list provided in [Appendix A](#)) at any time during the treatment-emergent adverse event period will be summarized by biological function and treatment group whatever the baseline level and/or according to the following baseline status categories:

- Normal/missing.
- Abnormal according to PCSA criterion or criteria.

The proportion of patients with key PCSA values at any time during the treatment-emergent adverse event period will also be displayed by duration of exposure for each treatment group.

For parameters for which no PCSA criteria are defined, similar table(s) using the normal range will be provided.

A listing of patients with at least one post-baseline PCSA will be provided and will display the whole profile over time at any time of all parameters of the corresponding biological function. In this listing, baseline, endpoint value and individual values will be flagged when lower or higher than the lower or upper laboratory limits and/or when reaching the absolute limit of abnormality criteria.

Drug-induced liver injury

The liver function tests, namely AST, ALT, alkaline phosphatase, and total bilirubin, are used to assess possible drug-induced liver toxicity. The proportion of patients with PCSA values at any postbaseline visit by baseline status will be displayed by treatment group for each parameter. The proportion of patients with PCSA values at any postbaseline visit will also be displayed by duration of exposure for each treatment group.

Time to onset of the initial ALT and AST elevation (>3 x upper limit of normal range [ULN]) and total bilirubin elevation (>2 x ULN) (time to first observation of ALT >3 x ULN or total bilirubin >2 x ULN, whichever comes first) will be analyzed using Kaplan-Meier estimates, presented by treatment group. Consideration should be given to the impact of the spacing of scheduled tests. A graph of distribution of peak values of ALT versus peak values of total bilirubin will also be

presented. Note that the ALT and total bilirubin values are presented on a logarithmic scale. The graph will be divided into 4 quadrants with a vertical line corresponding to 3 x ULN for ALT and a horizontal line corresponding to 2 x ULN for total bilirubin.

Listing of possible Hy's law cases identified by treatment group (eg, patients with any elevated ALT > 3 x ULN, and associated with an increase in bilirubin \geq 2 x ULN), presented with ALT, AST, alkaline phosphatase, total bilirubin, and the following complementary parameters: conjugated bilirubin and prothrombin time/international normalized ratio, creatine phosphokinase and serum creatinine.

Summarize the normalization by parameter (to \leq 1 x ULN or return to baseline) of elevated liver function tests by categories of elevation (3 x, 5 x, 10 x, 20 x ULN for ALT and AST, 1.5 x ULN for alkaline phosphatase, and 1.5 x and 2 x ULN for total bilirubin), with the following categories of normalization: never normalized, normalized despite treatment continuation of IMP, or normalized after IMP discontinuation. Note that a patient will be counted only under the maximum elevation category.

Proportion of patients with ALT > 1 x ULN and ALT > 2 x ULN at post-baseline visits will be presented by treatment group.

Summarize the incidence of liver-related adverse events by treatment group. The selection of preferred terms will be based on the hepatic disorder SMQ.

TSH

TSH will also be summarized for each study assessment by treatment group.

